6.1 Schedule of Procedures and Observations

Screening assessments must be performed within 8 weeks prior to the first dose of neoadjuvant androgen deprivation therapy. Any results falling outside of the reference ranges may be repeated at the discretion of the investigator. All on-study visit procedures are allowed **a window of ± 14 days** unless otherwise noted. Treatment or visit delays for public holidays or weather conditions do not constitute a protocol violation.

A written, signed, informed consent form (ICF) and a Health Insurance Portability and Accountability Act (HIPAA) authorization must be obtained before any study-specific assessments are initiated. A copy of the signed ICF will be given to the subject and a copy will be filed in the medical record. The original will be kept on file with the study records.

All patients who are consented will be registered in OnCore[®], the UCSF Helen Diller Family Comprehensive Cancer Center Clinical Trial Management System (CTMS). The system is password protected and meets HIPAA requirements.

6.1.1 Pretreatment Period

Patients will be seen for an initial consultation for discussion of treatment options. Once the patient has consented to enrollment onto study, all pre-study assessments must be

completed and eligibility verified by the clinical research coordinator prior to initiation of study treatment.

The Screening procedures and assessments must be completed within 14 weeks of the Day 1 Visit unless otherwise noted below.

- Detailed history and physical exam including height, weight, and baseline evaluation of symptoms, pain, and medications
- Baseline urinary, bowel, and sexual function will be assessed with the EPIC-26, PROMIS, and EQ-5D Questionnaires
- Liver transaminases for patients undergoing androgen deprivation therapy. AST or ALT must be < 2x upper limit of normal within 60 days of initiating androgen deprivation therapy.
- Total bilirubin
- MRI pelvis and prostate to define the extent of disease as part of routine staging for high risk prostate cancer and to aid in treatment planning.
- PSA should be obtained before or at least 20 days after prostate biopsy. The PSA half-life is approximately 2.2 days. The 20-day period will allow for approximately 9 half-lives to elapse, thus minimizing the flare effect from biopsy on actual PSA value. Also, every effort should be made to obtain all serum PSA values within the year prior to treatment for calculation of PSA kinetics.
- Testosterone level
- CBC with differential
- Basic metabolic panel
- Hepatitis B and C testing
- Fasting lipid panel, glucose level, and HbA1c
- Patients must also undergo 50 mL blood sample collection. Blood collection should be performed at time of PSA, testosterone, or other lab testing.
- TRUS biopsy – may be completed up to 25 weeks prior to enrollment.
- Collection of archival tissue from a prior prostate biopsy if available
- NaF PET/CT or Tc99m bone scan

6.1.2 4-6 weeks after initiation of Androgen Deprivation Therapy

- PSA level
- Testosterone level
- CBC with differential
- Basic metabolic panel
- AST, ALT, and total bilirubin
- Patients will undergo 50 mL blood collection at the time of lab testing.
- AE assessment
- After PSA testing, patients should undergo fiducial marker placement to optimize patient positioning and account for prostate motion during radiation treatment. During the fiducial marker procedure, a biopsy of the dominant lesion(s) should be

obtained. The additional risks and discomfort of the limited biopsy during the fiducial marker placement are minimal and include bleeding as a needle is already being introduced under ultrasound guidance for fiducial marker placement as part of the standard of care. If available, the biopsy should be mapped under MRI-guidance.

- Refer to section 5.0 for details regarding androgen deprivation therapy.

6.1.3 8 weeks after initiation of Androgen Deprivation Therapy

- Refer to section 4.0 for details regarding radiation therapy.
- Patients should complete the EPIC-26, PROMIS, and EQ-5D questionnaires up to 5 days before the first day of radiation therapy.
- AE assessment - all patients will undergo weekly assessment by the radiation oncologist for any signs of acute toxicity
- After 5 weeks of conventional whole pelvic radiotherapy, patients should complete the EPIC-26, PROMIS, and EQ-5D questionnaires.
- After 5 weeks of conventional whole pelvic radiotherapy, brachytherapy may be performed as part of the radiation boost procedure (phase 2). At the time of brachytherapy, a biopsy of the dominant lesion(s) may be performed. The risks and discomfort of the limited biopsy are minimal as multiple catheters (larger in diameter) are already being introduced under ultrasound guidance into the prostate as part of the HDR procedure.
- After 5 weeks of conventional whole pelvic radiotherapy and within the first 3 days of phase 2 boost procedure (days 1-3), 50 ml blood collection will be performed.

6.1.5 Discontinuation of Therapy

If a patient experiences a \geq Grade 3 toxicity or an intolerable side effect, withhold dosing for one week and until symptoms improve to \leq Grade 2, then resume at the same or a reduced dose (120 mg or 80 mg), if warranted.

In addition, the following safety/compliance events will result in the removal of patients from therapy either permanently or until the etiology of the problem has been identified and resolved:

- Any adverse event that is intolerable to the patient and that cannot be ameliorated by the use of adequate medical intervention, or that in the opinion of the investigator would lead to undue risk to the patient if dosing continued.
- Any seizure
- Creatinine >4.0 mg/dL
- Liver function tests (AST, ALT, or total bilirubin) >2 times the upper limit of normal
- An absolute neutrophil count $\leq 750/\mu\text{L}$
- A platelet count of $<50,000/\mu\text{L}$
- Patients who are in the opinion of the investigator or the medical monitor non-compliant with the protocol's requirements

The Investigator will withdraw a patient whenever continued participation is no longer in the patient's best interests. Reasons for withdrawing a patient include, but are not limited to, disease progression, the occurrence of an adverse event or a concurrent illness, a patient's request to end participation, a patient's non-compliance or simply significant uncertainty on the part of the Investigator that continued participation is prudent. There may also be administrative reasons to terminate participation, such as concern about a patient's compliance with the prescribed treatment regimen.

Table 6: Schedule of Assessments

| Study Assessments | Pre-Radiation Treatment | | During Radiation | Post-Radiation Treatment |
|--|-------------------------|--|---|--|
| | Baseline (Diagnosis) | 4-6 week after initiation of ADT (at placement of fiducial marker) | At Time of Brachytherapy Procedure (After fractionated whole pelvic radiotherapy) | Each follow up visit (6 wk, month 3-4, month 6, month 12, month 18, month 24, and month 36) ^a |
| Detailed medical history and physical exam | X | | | X (pertinent interval history and physical exam) |
| Collection of archival biopsy tissue if available | X | | | |
| TRUS biopsy of dominant lesion(s) ^b | X | X | X | |
| Serum PSA, testosterone | X | X | X | X |
| CBC with differential | X | X | X | X |
| Basic Metabolic Panel | X | X | X | X |
| Liver Function Tests including AST, ALT, and Total Bilirubin | X | X | X | X |
| Hepatitis B and C Testing | X | | | |
| Fasting Lipid Panel, glucose level, and HbA1c | X | | | X |
| 50 mL blood sample collection | Y | Y | Y | Y (month 3-4) |
| MRI prostate and pelvis | X | | | X (At time of PSA failure) |
| NaF PET/CT or Tc99m Bone Scan | X | | | X (At time of PSA failure) |
| EPIC-26, PROMIS, EQ-5D | X | | X (Before start of radiation therapy and after 5 weeks of conventional pelvic radiotherapy) | X |
| AE assessments | | X | Each week during external beam radiation therapy | X |

X = Assessments as determined by standard of care; Y = Additional procedure as part of study

^a Patients will be assessed at 6 weeks after completion of radiotherapy and then at least every 6 months thereafter for the first 2 years.

^b TRUS biopsies are optional and at provider discretion

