3.1 Characteristics

This is a phase II study to evaluate the safety, toxicity, and feasibility of the addition of enzalutamide to leuprolide for a total duration of 24 months in patients with high-risk prostate cancer or pelvic node positive disease receiving radiotherapy. High-risk prostate cancer is defined as 2 or more of the following characteristics: 1) cT3a/b, 2) PSA ≥ 20 and < 150 , 3) Gleason 8-10, and 4) $\geq 33\%$ core involvement.

Pre-Radiation Treatment

To be eligible, patients must have biopsy proven prostate cancer. MRI/US fusion-guided biopsy is encouraged, but not mandatory, of the dominant lesion(s), if available. Patients must also undergo serum PSA and testosterone measurement < 45 days prior to biopsy or at least 18 days after biopsy. The serum PSA half life is 2.2 days, therefore any elevation due to biopsy or instrumentation of the prostate should resolve by 18 days (> 5 half-lives). Patients must undergo blood sample collection prior to initiation of androgen deprivation therapy. All patients should complete the EPIC-26, PROMIS, and EQ-5D questionnaires prior to enrollment. Enrollment will begin once standard staging including above studies are completed.

4-6 wks after initiation of ADT

Patients will undergo repeat PSA and testosterone testing at 4-6 weeks after initiation of ADT. Blood collection should be performed at the time of PSA and testosterone testing. Patients should undergo fiducial marker placement to optimize patient positioning and account for prostate motion for future radiation treatment. During the fiducial marker procedure, a biopsy of the dominant lesion(s) will be obtained. The risks and discomfort of the limited biopsy are minimal as a needle is already being introduced under ultrasound guidance for fiducial marker placement as part of the standard of care. The biopsy should be mapped under MRI-guidance if available.

At time of brachytherapy (if being performed)

After 5 weeks of conventional whole pelvic radiotherapy, brachytherapy may be performed. At the time of brachytherapy, a biopsy of the dominant lesion(s) will be performed. The risks and discomfort of the limited biopsy are minimal as multiple catheters (larger in diameter) are already being introduced under ultrasound guidance into the prostate as part of the HDR procedure. Patients should complete the QOL questionnaires including EPIC-26, PROMIS, and EQ-5D.

Post-Radiation Therapy

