3.7.2 Study Completion

Study completion is projected approximately 60 months from the time the study is open to accrual.

4 Radiation Therapy

Radiation therapy should begin approximately 8 weeks (+/- 1 week) after the date of the first LHRH agonist/antagonist injection of hormone therapy is given.

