4.1.2. Phase 2: Reduced volume to boost prostate and seminal vesicles

Acceptable Treatment Modalities: IMRT, Stereotactic body radiotherapy, permanent prostate implant (PPI) brachytherapy or high-dose rate (HDR) brachytherapy

Table 2: Treatment Modalities and Prescription Dose for Phase 2

| Acceptable Treatment Modalities | Prescription Dose |
|---------------------------------------|--|
| Intensity-Modulated Radiotherapy | 34.2 Gy in 19 fractions of 1.8 Gy each |
| Stereotactic Body Radiotherapy | 19 Gy in 2 fractions of 9.5 Gy each |
| Permanent Prostate Seed Implant (PPI) | 
 • 108 Gy for I-125 • 90 Gy for Pd-103 |
| HDR brachytherapy | 15 Gy in one fraction |

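### Table 6 ties the only on-radiation safety labs to an optional brachytherapy procedure, so a patient boosted with IMRT has no protocol-scheduled safety labs for about 16 to 20 weeks

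*Combined protocol and SAP*

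**What the plan says.** Table 6 has four columns: baseline, "4-6 week after initiation of ADT (at placement of fiducial marker"), a single column under the During Radiation header, and follow-up visits, the first of them 6 weeks after radiotherapy ends. The During Radiation column is headed "At Time of Brachytherapy Procedure (After fractionated whole pelvic radiotherapy"). The safety-lab rows are marked in all four columns, for example "CBC with differential | X | X | X | X"; the basic metabolic panel and liver-test rows follow the same pattern.

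Brachytherapy is not mandatory. Section 3.1 introduces that time point as "At time of brachytherapy (if being performed"), and sections 6.1.3 and 8.1.2 are also conditional. Table 2 in section 4.1.2 accepts a stereotactic boost and an IMRT boost of "34.2 Gy in 19 fractions of 1.8 Gy each". Sections 4.5 and 4.6 restrict implants by prostate volume, and section 4.6 also by TURP defect.

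Sections 6.1.2 and 6.1.4 list the CBC, metabolic panel and liver tests in the text. Section 6.1.3, between them, does not. It lists questionnaires, weekly adverse-event assessment, an optional biopsy and a research sample: "within the first 3 days of phase 2 boost procedure (days 1-3), 50 ml blood collection will be performed".

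Section 6.1.5 removes patients from therapy, permanently or until the problem is resolved, on laboratory limits for creatinine, neutrophils and platelets, and on "Liver function tests (AST, ALT, or total bilirubin) >2 times the upper limit of normal".

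**The concern.** A laboratory removal limit works reliably only if a test is due. For a patient boosted with IMRT or stereotactic radiotherapy, the column holding the on-radiation tests names a procedure that does not take place, and the text for that period does not supply the tests. A site following the schedule literally would have no instruction to draw them.

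The period matters because section 1.2 states that enzalutamide plus an LHRH agonist with concurrent radiation has not been reported, and safety of the combination is a primary objective (section 2.1). Section 7.2 plans shift tables from baseline to on-treatment values, and section 9.4.2 reports one pooled rate of grade 3 or greater toxicity. If the on-radiation panel is due for some boost types only, the laboratory part of that safety record is collected unevenly.

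**Working it through.** The documents state no interval without labs, so there is no figure to reproduce. The building blocks agree with the plan: 25 × 1.8 = 45.0 Gy (section 4.2.2.1), 19 × 1.8 = 34.2 Gy (Table 2), and the sum is 79.2 Gy (section 4.3).

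**Inputs**
- Last scheduled labs before radiotherapy: week 4-6 of ADT, taken as day 28-42.
- Start of radiotherapy: day 53-67 in the study schema. Section 4 says "Radiation therapy should begin approximately 8 weeks (+/- 1 week) after the date of the first LHRH agonist/antagonist injection", which is day 49-63.
- IMRT course: 25 + 19 = 44 weekday fractions. From a Monday start the last falls 59 days later (61 days from a Wednesday to Friday start).
- Next scheduled labs: 42 days after radiotherapy ends (section 6.1.4).
- Enzalutamide: 24 months (section 5.1.1), so it spans the interval unless interrupted.

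**Formula:** gap = start day + days to last fraction + 42 − day of the week 4-6 labs.

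**IMRT boost, schema start**
- Shortest: 53 + 59 + 42 − 42 = 112 days = 16.0 weeks.
- Longest: 67 + 59 + 42 − 28 = 140 days = 20.0 weeks (142 days, 20.3 weeks, with a later-weekday start).

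**IMRT boost, section 4 start**
- Shortest: 49 + 59 + 42 − 42 = 108 days = 15.4 weeks.
- Nominal: 56 + 59 + 42 − 35 = 122 days = 17.4 weeks.
- Longest: 63 + 61 + 42 − 28 = 138 days = 19.7 weeks.

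**Split of the nominal 122 days:** 21 days before radiotherapy (3 weeks), 59 days on radiotherapy (8.4 weeks, of which 5 are pelvic and the rest prostate boost) and 42 days after it (6 weeks).

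**Stereotactic boost** (2 fractions, assumed on consecutive weekdays straight after the 25): the last fraction is 36 to 38 days after the start. Shortest: 49 + 36 + 42 − 42 = 85 days = 12.1 weeks. Longest: 67 + 38 + 42 − 28 = 119 days = 17.0 weeks.

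**Brachytherapy, for comparison** (implant assumed 35 days after the start): the first interval runs from 49 + 35 − 42 = 42 days (6.0 weeks) to 67 + 35 − 28 = 74 days (10.6 weeks). The follow-up labs come 6 weeks after the implant.

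**Sensitivity of the IMRT figure**
- The ±14-day window of section 6.1 on both visits: 108 − 28 = 80 days to 142 + 28 = 170 days, about 11 to 24 weeks.
- The 9-fraction nodal boost of section 4.2.2.2, if given in series: about 17 to 22 weeks.
- The synopsis figure of 15 treatment days for the first phase, which disagrees with 25 fractions: about 13 to 18 weeks.

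**Other draws inside the gap.** Section 2.4.1 sets a draw at day 120-127 for PSA only. The 50 mL research sample goes with the boost procedure in section 6.1.3 but with brachytherapy in section 8.1, and Table 6 places it in the same brachytherapy column. Neither draw is linked to safety labs in the text.

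**The case against.** The column may simply be loosely labelled. It sits under During Radiation, its heading also refers to the end of pelvic radiotherapy, and its questionnaire and adverse-event cells are not specific to brachytherapy. The synopsis describes a brachytherapy boost as the study treatment, so the heading may name the expected pathway and the authors may have meant every patient. This is plausible, but neither the heading nor section 6.1.3 says so for the labs. It is a reason to correct the wording.

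A reader might infer that these patients have no blood tests at all and that the section 6.1.5 limits cannot act. The documents do not support that. The Table 6 legend marks the tests as standard of care, a radiation oncologist sees every patient weekly during external beam treatment, and the limits are not confined to scheduled results. What is absent is a protocol-scheduled test.

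A reader might also take the 16 to 20 weeks as time on pelvic radiotherapy. Only about 5 of them are, and during those weeks brachytherapy patients have no scheduled labs either, because the column falls after pelvic treatment. The modalities differ from the end of pelvic radiotherapy onward.

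Finally, a reader might infer that the pooled toxicity rate is biased. No boost mix is given. The 12% benchmark comes from GU and GI toxicity, and section 3.4 counts only clinically significant, treatment-related events. All patients also have labs 6 weeks after radiotherapy, inside the 90-day acute window of section 2.4.1. Uneven ascertainment stands; a material effect on the rate is not shown.

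**Conclusion.** The point holds as a gap in the schedule that should be corrected. As written, an IMRT-boosted patient goes about 16 to 20 weeks without protocol-scheduled safety labs, and a patient with a stereotactic boost about 12 to 17 weeks. For IMRT, about 8 to 9 of those weeks are on radiotherapy. Over that time the laboratory removal limits rest on unscheduled local practice in these patients, and laboratory toxicity is looked for differently by boost type. The size of any effect on the reported toxicity rate is unknown.

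This rests on a literal reading of the Table 6 heading, five fractions a week without breaks, week 4-6 taken as day 28-42, and no use of the visit windows. The other stated start range moves the IMRT figure by less than a week. The number of patients affected cannot be derived from the documents.

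**What to change.** Reconcile Table 6 with sections 6.1.3, 4.1.2, 6.1.5 and 8.1, so that the on-radiation CBC, metabolic panel and liver tests already in the table do not depend on boost modality and section 6.1.3 agrees with the table. In the same amendment, settle whether the 50 mL sample goes with the boost procedure of any type (section 6.1.3) or with brachytherapy only (section 8.1). The sponsor sets the timing, and the section 6.1.5 limits are untouched.

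When choosing the timing, note that a panel at the end of pelvic radiotherapy would still leave an IMRT patient 59 + 42 − 35 = 66 days (9.4 weeks) to the first follow-up labs.

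The cost is amendment wording and at most one routine panel per non-brachytherapy patient. It may also need one extra blood draw, because a research venepuncture at that time is not assured for these patients until sections 6.1.3 and 8.1 agree.

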2.2 Secondary

1. To determine time to biochemical failure as determined by the ASTRO Phoenix definition of nadir + 2 ng/mL, local progression, regional progression, and distant metastases.
2. To determine time to clinical progression free survival
3. To assess PSA nadir and PSA and testosterone levels at 3-4, 6, 12, and 24 months.
4. To assess changes in HbA1c, fasting glucose, fasting insulin and fasting lipid and cholesterol levels.

5. To document changes in quality of life outcomes.

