2.4.2 Secondary Endpoints

1. PSA and testosterone measurements will be made at 6 weeks and then at 3-4 months, 6 months, 12 months, 18 months, 24 months, and at 36 months as part of standard of care. The time to biochemical failure will be defined from the date of randomization to the date of a rise by ≥ 2 ng/mL from the nadir PSA per the Phoenix Definition. PSA nadir and PSA and testosterone levels will be documented at 4, 6, 12, and 24 months.
2. The time to local failure will be defined from the date of randomization to the date of biopsy proven recurrence within the prostate gland.
3. The date of regional or distant metastases will be defined as the date from randomization to the date of imaging or biopsy demonstrated evidence for recurrence in the pelvic lymph nodes (regional) or systemically. Biopsy is not required to define regional or distant metastasis; however, in absence of rising PSA, biopsy is encouraged.
4. The time to clinical progression will be defined from the date of randomization to the date of PSA failure, local failure, regional or distant metastases. Deaths prior to any of these events are treated as censoring for this endpoint.
5. Changes in HbA1c, fasting glucose, fasting insulin and fasting lipid and cholesterol levels will be assessed at 12 and 24 months during treatment.
6. Quality of life will be monitored. Changes in patient reported quality of life would be measured by the Expanded Prostate Cancer Index Composite (EPIC).

Changes in fatigue from baseline to 1 year will be measured by PROMIS. Assessment of quality adjusted survival will be performed using the EQ-5D.

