8.1 Specimen Collection Summary for Translational Research

| Specimens Taken From Patient | Time of Collection |
|--|--|
| Diagnostic Core Biopsy Specimen(s) | 1) Pre-treatment 2) 4-6 wks after initiation of androgen deprivation therapy (at time of fiducial marker placement) 3) At the time of brachytherapy (if brachytherapy is being performed) |
| Whole blood: 50 mL of whole blood will be collected into green top tubes (sodium heparin). This should be collected, if possible, at the time of each blood draw for PSA and testosterone. | 1) Pre-Treatment 2) 4-6 wks after initiation of androgen deprivation therapy (at time of fiducial marker placement) 3) Within first 3 days of phase 2 brachytherapy 4) Month 3-4 post-radiation therapy |

Core biopsy specimens will be snap frozen in liquid nitrogen and stored at -80°C.

Plasma and whole blood samples will be processed and stored frozen at -80°C.

All samples will be de-identified and labeled with a case number. Samples will be sent frozen on dry ice via overnight carrier stored in a locked -80 °C freezer.

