9.4.3 Secondary Analysis (or Analysis of Secondary Endpoints)

The time to local failure will be defined from the date of randomization to the date of biopsy proven recurrence within the prostate gland. The distribution of the time to event data will be estimated by Kaplan-Meier method.

The time to clinical progression will be defined from the date of randomization to the date of PSA failure, local failure, regional or distant metastases. Deaths prior to any of these events are treated as censoring for this endpoint. The distribution of the time to event data will be estimated by Kaplan-Meier method.

To assess PSA nadir, PSA, testosterone levels, HbA1c, fasting glucose, fasting insulin and fasting lipid and cholesterol levels at each time point, the summary statistics for continuous variables will be used.

To assess their changes across the time, the random effect model for longitudinal data will be used for each outcome measurement.

Patient-reported quality of life outcomes will be assessed by EPIC, PROMIS, and EQ-5D questionnaires and will be described by summary statistics for categorical data.

10 Study Management

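### Fasting insulin is part of a secondary change endpoint, but no assessment list orders it: no baseline draw is scheduled, and the 12- and 24-month assessments appear only in the endpoint text

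*Combined protocol and SAP*

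**What the plan says.** Four places commit the trial to fasting insulin. The synopsis lists it among the secondary objectives, and section 2.2 repeats it as objective 4: "To assess changes in HbA1c, fasting glucose, fasting insulin and fasting lipid and cholesterol levels". Section 2.4.2, item 5, turns this into an endpoint with times: "Changes in HbA1c, fasting glucose, fasting insulin and fasting lipid and cholesterol levels will be assessed at 12 and 24 months during treatment". Section 9.4.3 plans the analysis, first as summary statistics ("To assess PSA nadir, PSA, testosterone levels, HbA1c, fasting glucose, fasting insulin and fasting lipid and cholesterol levels at each time point") and then, for change over time, by stating that "the random effect model for longitudinal data will be used for each outcome measurement".

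Three places schedule the metabolic laboratory work. Section 6.1.1, for the pretreatment period, lists "Fasting lipid panel, glucose level, and HbA1c". Section 6.1.4, for each follow-up visit, lists the same items. Table 6 has a single metabolic row, "Fasting Lipid Panel, glucose level, and HbA1c", marked at baseline and at each follow-up visit. None of the three includes insulin.

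**The concern.** An endpoint defined as a change needs a starting value. HbA1c, glucose and lipids each have one, because the pretreatment list orders them. Insulin does not. Once androgen deprivation has begun, a fresh draw can no longer give a pretreatment value, so each patient who starts without one is lost to the change-from-baseline analysis of this analyte.

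The second risk is practical. Coordinators work from the visit lists and Table 6, and section 10.6 says that data are entered on case report forms following the study calendar. A test named only in the endpoint section is easily left off the laboratory order and may have no field to be recorded in. The 12- and 24-month values are then at risk as well.

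**Working it through.** No power, alpha or sample-size calculation bears on this, and the plan gives no figure to reproduce. The check sets every mention of fasting insulin against every list of assessments.

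**1. Where each component is named and where it is ordered**

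| Place | HbA1c, glucose, lipids | Insulin |
|---|---|---|
| Synopsis, secondary objectives | yes | yes |
| 2.2, objective 4 | yes | yes |
| 2.4.2, item 5 | yes | yes |
| 9.4.3 | yes | yes |
| 6.1.1, pretreatment | yes | no |
| 6.1.4, follow-up | yes | no |
| Table 6 | yes | no |

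Insulin appears in 4 of 4 statements of intent and 0 of 3 metabolic lists. Its companion measures appear in all seven. The lists for 4-6 weeks (6.1.2) and 8 weeks (6.1.3) after the start of androgen deprivation do not include insulin either.

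**2. Whether another listed test supplies it.** The remaining laboratory items are the blood count, basic metabolic panel, liver tests, PSA, testosterone and hepatitis testing. The protocol does not describe any of them as including insulin.

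**3. Whether the research blood supplies it.** Section 8.1 says that "50 mL of whole blood will be collected into green top tubes (sodium heparin". The draws are pretreatment, at 4-6 weeks, at the boost, and at month 3-4 after radiotherapy. They are not stated to be fasting, no insulin assay is planned on them, and none falls at 12 or 24 months.

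**4. What can be estimated.** Write the values as I0 (pretreatment), I12 and I24. The changes from baseline are I12 − I0 and I24 − I0. I0 is scheduled nowhere, so neither can be formed. If sites act on 2.4.2, I12 and I24 exist. Summaries at those two times and the difference I24 − I12 are then available, and the random effect model can describe that interval only.

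**5. Size of the repair.**
- Insulin at the times the endpoint needs: baseline, 12 and 24 months = 3 per patient; 3 × 53 = 159 assays.
- Insulin added without limit to the list in 6.1.4, which applies at all seven follow-up visits: 1 + 7 = 8 per patient; 8 × 53 = 424 assays. The extra 424 − 159 = 265 would serve no stated time point.

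**6. Which month 12 and month 24.** Section 2.4.2 speaks of months during treatment, whereas 3.6 counts follow-up visits from the end of radiotherapy. Radiotherapy starts about 8 weeks after the first injection and its pelvic phase lasts 5 weeks, so the visit clock starts about 8 + 5 = 13 weeks (roughly 3 months) into drug treatment. The month-24 visit is therefore about 24 + 3 = 27 months after drug treatment begins, beyond the 24-month course. This applies to all the metabolic measures, but it affects where an insulin entry is placed.

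**The case against.** The strongest reply is that section 2.4.2 is itself operative protocol text. It says insulin will be assessed at 12 and 24 months, so a site that reads the whole protocol has an instruction and dates for two draws. This stands. A reader might infer from Table 6 that insulin will be entirely missing and that the model in 9.4.3 will have nothing to analyse. The documents do not support that reading: on-treatment values are called for, even though the visit lists omit them. The study calendar and case report forms are also not in the document, so what is actually collected is unknown.

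A second reply is that pretreatment research blood is drawn and section 8.1 provides for frozen plasma, so a baseline might be salvaged. This stands only in part. A stored sample may exist, but it is not stated to be fasting and no insulin assay is planned on it. It is a possible rescue, not a scheduled measurement.

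A third reply is that little depends on insulin. It is one analyte within one of six secondary endpoint items, with no hypothesis, threshold or power attached. This also stands and limits the weight of the point. None of the three replies supplies a scheduled baseline.

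**Conclusion.** The endpoint and the schedule contradict each other. As scheduled, the trial has no baseline fasting insulin and cannot estimate change from baseline for that analyte. The 12- and 24-month values rest on the endpoint text alone and are at risk where sites work from Table 6.

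The conclusion rests on two assumptions. The first is that change means change from the pretreatment value. Section 2.4.2 does not name the reference point, but the pretreatment draw of the companion measures points that way. The second is that the unseen study calendar follows the printed lists.

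The consequence is limited to one component of one secondary endpoint. The PSA complete response and toxicity endpoints, the sample size, and the HbA1c, glucose and lipid analyses are unaffected.

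**What to change.** **If insulin is to be measured:** add it to the fasting draw already listed at baseline (6.1.1) and to the 12- and 24-month draws in 6.1.4, not to every follow-up visit. Give it its own entry in Table 6. The existing metabolic row is marked X, the code for standard of care; if insulin is not standard of care, mark it Y, the code for a study procedure. State in 2.4.2 that change is measured from the pretreatment value, and say whether the 12 and 24 months run from the start of drug treatment or from the end of radiotherapy. Add a field to the case report form.

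The cost is three assays per patient, at most 159 for 53 patients. No new visit is needed if the two times are the existing month-12 and month-24 follow-up visits. Report patients who began treatment without a baseline value as missing it.

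**If insulin will not be measured:** delete it from all four places (synopsis, 2.2, 2.4.2 and 9.4.3). Leaving the synopsis unchanged would keep the inconsistency. This costs only the text of an amendment.
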